2.2 Scientific Rationale

2.2.1 Predictive Model Approaches

There has been increased interest in developing predictive models for PCN (B-lactam) allergy. Santurino¹⁹ employed a retrospective model to assess 466 patients from Salamanca, Spain who were evaluated for *any* adverse drug reaction (ADR) (only 27% were B-lactams). A multivariate model was constructed which found that the significant variables were age at time of reaction and symptoms suggestive of allergic disease. However, this study is limited because it was a relatively small sample, retrospective, assessed older patients with multiple comorbidities and medications, and assessed ADRs in general, not specific to B-lactams. It also started from the vantage point of individuals who were already diagnosed with an ADR, as opposed to those who had histories which are more likely to be remote.

A more robust approach was undertaken by Chiriac²⁰ who attempted to design a predictive model more specifically for B-lactam allergy, using patient populations with high prevalence of confirmed B-lactam allergy (26-31%). In the initial phase of the model development, they used retrospective patient data (training set) with 1991 patients. Of these, urticarial/angioedema was the most common symptom (43.5%). Interestingly, in the multivariate analyses, atopy and asthma were not associated. The significant factors for B-lactam allergy were immediate reaction, age (younger) at time of reaction, anaphylaxis and multiple episodes. After the model was developed, the authors adapted this to a prospective sample of 200 patients (validation set). Optimizing the model using different variable weights found that the model with the highest sensitivity was 98% in both the training and validation sets, but with an NPV of 77% in the retrospective training set and 85% in the prospective sample. Although this study highlights present dilemmas in accurate diagnosis of allergy without clinical testing, Blumenthal in, an

accompanying editorial,²¹ points out that 1) this was a population with very high prevalence of true allergy; and 2) in typical outpatient clinic populations, the allergy prevalence is much lower than Chiriac's populations. Therefore, we would anticipate that the NPV would be much higher. Since our intent in this study is to develop algorithms which have high NPVs, this supports our hypothesis.

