Many experienced clinicians attempt to differentiate hypersensitivity from non-allergic reactions (i.e., non-allergic drug toxicity) by taking a careful history of the drug toxicity event(s). However, in the STD clinic setting, this may not be practical because of the wide variety of skills sets and expertise in these clinics. Because many clinics may not have physicians on staff 100% of the time and are ambulatory sites, there is a clear need to develop a path for an easy to administer instrument and testing algorithm that can be administered to patients who report a history of PCN (B-lactam) allergy. The instrument should have high sensitivity (for discerning which patients have true hypersensitivity) and a high NPV in clinic settings (important for clinicians and management) to enable B-lactam use to optimize treatment for a meaningful percentage of subjects who do not have allergy.

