6.2 PCN Skin Testing

Depending on the outcome of the PCN (B-lactam) allergy history screening questionnaire, participants may qualify to receive the PCN skin test.

- Participants with a higher risk of PCN allergy will not proceed to the PCN skin test or oral challenge. Their study participation will be complete. Subjects will be provided with a written referral to local allergy providers.
- Participants with a low risk of PCN allergy and assigned to the PST intervention group will be offered the PCN skin test.

Staff will verify that qualified participants do not meet any additional criteria that would preclude them from skin testing using the Skin Test Qualification Checklist. Study staff will explain the skin testing procedures to participants who may decide to accept or decline skin testing. If they decline, they will be asked to complete the subject acceptability survey and their study participation will be complete. Staff will note the reason(s) they declined to be skin tested on the appropriate CRF.

Study staff will perform the allergy skin testing for PCN allergy in accordance with standard allergy testing procedures and instructions provided in the PRE-PEN® kit package insert.³¹ Prick (Puncture) tests will be performed before proceeding to intradermal testing. Prick testing is performed at marked sites on the inner volar aspect of the forearm. Testing for controls and each reagent is performed singly.

Reagents and controls for prick and intradermal tests include:

1. Controls:
 - a.) Negative Control: Sodium chloride solution without preservative

* e.g., patients presenting with secondary syphilis

- b.) Positive Control: Histamine:
 - i. Prick testing: histamine base 1 mg/ml
 - ii. Intradermal testing: histamine base 0.1 mg/ml
2. Reagents:
 - a.) PRE-PEN® (major determinant)
 - b.) Penicillin G 10,000 U/ml (minor determinant)

Intradermal testing will not be performed if there is a positive or uninterpretable reaction to PRE-PEN® and/or Penicillin G during the prick test. If the prick skin test results are negative the participant is qualified for intradermal testing. Study staff will perform duplicate intradermal skin testing of each reagent and single intradermal skin testing of the positive and negative controls on the inner volar aspect of the forearm. The same arm will be used for both prick and intradermal testing.

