8.4.1 Primary analysis

The primary analysis will estimate with corresponding exact 95% confidence intervals:

- The prevalence of PCN reactivity validated either by skin test or by direct oral challenge among those participants who report a history of PCN (B-lactam) allergy and who have low-risk histories.
- The NPV on true PCN (B-lactam) allergy of the algorithm / PCN (B-lactam) allergy history screening questionnaire performance in the study population.

The NPV for each question will be estimated and its performance will be assessed.

To construct a short standardized post-study questionnaire (4-6 questions) from the PCN (B-lactam) allergy history screening questionnaire, we will use Item Response Theory (IRT) to evaluate each question item's discrimination ability of true PCN (B-lactam) allergy and use variable importance evaluation functions to indicate which questions are most useful for

predicting the true PCN (B-lactam) allergy. Based on the results of IRT and variable importance analyses, we will then apply machine learning approaches (e.g., random forest approach via R packages of caret)³³ to select a short post-study questionnaire that has the highest NPV among those possible short questionnaires with 4-6 selected questions.

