APPENDIX B: PCN (B-LACTAM) ALLERGY HISTORY SCREENING QUESTIONNAIRE

Section 1: Allergy History

- 1) How long ago was the reaction to the antibiotic?
 - a. < 6 months
 - b. 6 months-1 year
 - c. 2-5 years
 - d. 6-10 years
 - e. > 10 years
 - f. Don't remember / Unknown

- 2) What was the name of the drug you reacted to?
 - a. (Please list) _____
 - b. Don't remember / Unknown

- 3) How was the antibiotic administered?
 - a. Pill or Liquid by mouth
 - b. Injection (a shot) into a muscle or through a vein
 - c. Don't remember / Unknown

- 4) When did your allergic reaction to the antibiotic start?
 - a. Less than 1 hour after the first dose
 - b. Between 1 and 6 hours after the first dose
 - c. More than 6 hours, but less than 24 hours after the first dose
 - d. 24 hours or more after the first dose
 - e. Unknown

- 5) How many days did you receive your antibiotic treatment?
 - a. One day only
 - b. About _____ days of treatment
 - c. Don't remember / Unknown

- 6) People experience many different kinds of symptoms during an allergic reaction to an antibiotic. What were the symptoms of your allergic reaction? (OK to select more than one)
 - a. Can't remember (check only after reading entire list)

- b. Non-specific symptom(s) (e.g., "sick" "thought I was a goner" "high as a kite" "like I had the flu")

Responses to the symptoms listed below should be graded on a 5-point scale:

Don't Recall /None / Mild / Moderate / Severe

Low-Risk Allergy History

- a. Isolated GI upset (*diarrhea, nausea, vomiting, abdominal pain*)
- b. Chills (*rigors*)
- c. Headache
- d. Fatigue
- e. Itching (*pruritus*), self-limited,
- f. Rash (*including maculopapular rash*)
- g. Hives (greater than 5 years ago)
- h. Flushing / redness
- i. Family history
- j. Patient denies allergy history but is in medical record

Higher-Risk Allergy History: Skin Testing and Oral Challenge Contraindicated

- a. Angioedema or swelling of lip, tongue, or around eyes
- b. Wheezing / chest tightness moderate or severe shortness of breath
- c. Throat tightness which affected ability to breathe
- d. Hypotension without rapid recovery
- e. Arrhythmia / irregular heartbeat or palpitations
- f. Syncope / pass out / dizzy
- g. Anaphylaxis or sudden drop in blood pressure
- h. Hives (5 years or less)

Late Effect Symptoms (higher-risk events occurred >24 hours after drug administration)

- a. Stevens-Johnson syndrome (*Loss >10% of skin*)
- b. Organ injury (*liver, kidney*)
- c. Low Platelets

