2.1 Primary Objective

- Validate an algorithm which incorporates a PCN (B-lactam) allergy history screening questionnaire followed by an allergy validation intervention — 1) skin testing and oral challenge or 2) direct two-step oral challenge — to produce a short standardized post-study questionnaire (4-6 questions) for use in ambulatory STD settings.
- Determine how many subjects who report PCN (B-lactam) allergy can be treated with PCN or B-lactam drugs.

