7.3 Analysis of Primary Objective

The primary analysis will be performed on the Treated population and Per Protocol population. Estimates with corresponding exact (Clopper-Pearson) 95% confidence intervals for the following measures will be provided:

- The prevalence of PCN reactivity validated either by skin test or by direct oral challenge among those participants who report a history of PCN (B lactam) allergy and who have low-risk histories.
- The NPV on true PCN (B-lactam) allergy of the algorithm / PCN (B-lactam) allergy history screening questionnaire performance in the Treated population.

The NPV for each low-risk allergy item listed on the questionnaire will be estimated and will be compared with the prevalence of PCN reactivity using exact test of binomial proportion. The p-values will be adjusted with Benjamini-Hochberg procedure.

To construct a short standardized post-study questionnaire (4-6 questions) from the PCN (B-lactam) allergy history screening questionnaire, we will first use the item-characteristic curve from Item Response Theory (IRT) to evaluate each question item's discrimination ability of true PCN (B-lactam) allergy and use variable importance evaluation functions to indicate which questions are most useful for predicting the true PCN (B-lactam) allergy. Based on the results of IRT and variable importance analyses, we will then apply machine learning approaches such as random forest (Svetnik et al., 2003) via R package caret, to select a short post-study questionnaire that has the highest NPV among those possible short questionnaires with 4-6 selected questions.

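### The 4-6 question form is chosen by highest NPV alone, with no out-of-sample estimate, no definition of a negative result, and no reporting of sensitivity or share cleared

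*SAP*

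**What the plan says.** The short form is a deliverable of the primary objective: SAP 2.1 sets out "to produce a short standardized post-study questionnaire (4-6 questions) for use in ambulatory STD settings". SAP 7.3 first screens items by IRT and variable importance, then applies methods such as random forest through the R package caret "to select a short post-study questionnaire that has the highest NPV among those possible short questionnaires with 4-6 selected questions". Protocol 8.4.1 likewise says that it will "select a short post-study questionnaire that has the highest NPV among those" forms of 4-6 questions. No second criterion is given.

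NPV as the leading measure is deliberate. Protocol 2.2.1 states that "our intent in this study is to develop algorithms which have high NPVs". Protocol 2.2.6 goes further: "The instrument should have high sensitivity (for discerning which patients have true hypersensitivity) and a high NPV in clinic settings", so that B-lactams can be used in "a meaningful percentage of subjects who do not have allergy".

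SAP 7.3 lists two primary estimates with exact intervals: prevalence of reactivity, and NPV. It runs them on the Treated and Per Protocol populations. Only low-risk subjects can enter those populations, because Protocol 6.2 says: "Participants with a higher risk of PCN allergy will not proceed to the PCN skin test or oral challenge". The low-risk and higher-risk lists in Protocol 6.1.2.1 classify the full questionnaire, not the short form.

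**The concern.** Three things needed to interpret the short form are missing from both documents.

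- **Out-of-sample estimate.** Nothing mentions a hold-out set, cross-validation, bootstrap or optimism correction for the short form. Taking the largest NPV among many forms and reporting that same figure overstates it.
- **Negative rule.** Nothing says how 4-6 answers combine into a negative result, or which predicted probability is the cut-off. Without that, the NPV being maximised is not defined. The selection unit is open too: Appendix B places every symptom inside question 6 and says "Responses to the symptoms listed below should be graded on a 5-point scale", so a question could mean the whole of question 6 or one symptom.
- **Sensitivity and share cleared.** Neither is a planned output for the short form. At low prevalence NPV says little alone: at 3%, clearing everyone already gives 97%.

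At stake is the figure that clinics would rely on. If it comes from the selecting data, the form will perform less well in use than its published NPV suggests.

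**Working it through.** **The plan's own figure.** Inputs from SAP section 6: sensitivity 85%, specificity 95%, prevalence 3% in the population and in the study, power 85%, and 5% not tested.

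- NPV = 0.95×0.97 / (0.95×0.97 + 0.15×0.03) = 0.9215/0.9260 = 99.51%.
- On the log-odds scale with one-sided 5%, n = 7.189 × [0.85/(0.15×0.03) + 0.05/(0.95×0.97)] / [logit(0.9951) − logit(0.984)]² = 7.189 × 188.94 / (5.322 − 4.119)² = 939 tested. Then 939/0.95 = 988.

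Both figures reproduce. They describe one fixed classifier and make no allowance for choosing among forms.

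**Events available.** 1,000 less 5% gives 950 tested (assumed). Reactors: 9.5, 28.5 or 47.5 at 1%, 3% or 5%.

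**Candidate forms.** Ten whole questions in Appendix B, Section 1: C(10,4)+C(10,5)+C(10,6) = 210+252+210 = 672. Counting the ten low-risk symptoms of question 6 singly beside the nine other questions (19 items): 3,876+11,628+27,132 = 42,636. Screening by IRT or importance shortens the list, but that screening uses the same outcomes.

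**Direction.** For any pre-defined form, observed NPV is unbiased given the number cleared. The expected maximum over forms is at least the largest expected value, which is at least the true NPV of whichever form is picked. So the bias is upward.

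**Size, by simulation at 3%.** 950 tested; ten independent yes/no items, endorsed by 5-20% or 10-30% of subjects (ranges below span the two). There are either no real predictors or two with an odds ratio of 5. In the search of all 672 forms, cleared means no item endorsed. In the forest version, seven items are kept by importance and cleared means predicted probability at or below observed reactivity. Nested means that the selection is repeated inside 10-fold cross-validation.

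| Setting | NPV in selecting data | NPV in fresh data | Gap (points) | Nested NPV |
|---|---|---|---|---|
| All forms, two predictors | 99.1-99.7% | 98.5-98.9% | 0.6-0.8 | 98.5-98.8% |
| All forms, no predictors | 98.0-98.6% | 97.0% | 1.0-1.6 | 96.9-97.1% |
| Forest, two predictors, chosen on resubstitution NPV | 99.2-99.6% | 97.6-97.9% | 1.6-1.7 | not quoted |
| Forest, two predictors, chosen on out-of-bag NPV | 98.6-98.9% | 98.1-98.3% | 0.5-0.7 | 98.0-98.3% |

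Stronger predictors shrink the all-forms gap: about 0.4-0.5 (two, odds ratio 10), 0.5-0.6 (four, odds ratio 5) and 0.3-0.4 (four, odds ratio 10). Nested cross-validation comes close to the fresh-data value wherever it was run.

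**Why the negative rule matters.** In the same forest, a majority-vote cut-off clears 99.8-100% of subjects with sensitivity 0-1% and NPV about 97%, the same as using no form.

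**Why share cleared matters.** With no reactors among n cleared, the exact two-sided lower bound is 0.025^(1/n). It passes 97% at n = 122 (13% of 950) and 98.4% at n = 229 (24%). A form can therefore show a convincing NPV while clearing few people.

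**The case against.** **Random forests and caret can resample.** True, and it would be wrong to infer that the plan will report resubstitution NPV; it says nothing either way. The 1.6-1.7 point gap applies only on that reading. But the SAP does not say that the reported figure will come from resampling, or that the IRT and importance steps will be repeated inside it. Choosing on out-of-bag NPV without that repetition still leaves 0.5-0.7 points.

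**NPV is the intended criterion.** It is, and it should stay. What is missing is the reporting beside it that Protocol 2.2.6 calls for.

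**The population is already set.** Correct: SAP 7.3 and 4.4 give it. A reader might infer that the analysis population is undefined, but what is missing is only a label saying to whom the form's figures apply.

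**The sizes rest on assumed items.** This stands. The documents give no item frequencies or predictor strengths, the five-level grading was reduced to yes/no, and IRT was not simulated. Clearing people who endorse nothing may also not be the intended rule, since endorsing a low-risk symptom can itself be the negative answer. The figure of 950 could be nearer 1,000 if evaluable already means tested, or lower after the exclusions in Protocol 6.1.3 and refusals.

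**A tempting overreach** is that a worthless form could display the planned 99.51%. That happens only with wholly uninformative items and high assumed endorsement (10-60%), where the selected form averages 99.7%. Nothing in the documents supports those inputs.

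**Conclusion.** The omission is clear from the text and should be fixed. The short form's NPV is undefined until a negative rule is stated, and it is optimistic if taken from the data that chose the form. The upward direction does not depend on the simulation settings. The size does: roughly 0.3-1.7 points at 3% reactivity, against the planned gain of 99.51 − 97.0 = 2.5 points. Wholly uninformative items can give more (2.5 points for a forest chosen on resubstitution NPV), but that is a worst case, not an expectation.

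The point does not reach the prevalence estimate or the full-questionnaire NPV, because neither involves selection. Nor does it show that 988 is miscalculated for the fixed classifier it assumes. Confidence is high in the omission and moderate in the size.

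**What to change.** Amend SAP 7.3 and Protocol 8.4.1 before data freeze.

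1. State the selection unit (whole question or single symptom), its coding, and the rule for a negative result. The rule may be fixed, or it may be a fixed algorithm that derives a cut-off; if derived, it is re-derived inside each fold.
2. Keep NPV as the main criterion, but compare candidates on resampled NPV and report sensitivity and share cleared beside it. Any minimum for either is for the sponsor to set. In the 3% forest illustration, choosing on out-of-bag instead of resubstitution NPV gave 98.1-98.3% instead of 97.6-97.9% in fresh data and cleared about 74% instead of 53-65%.
3. Repeat every data-driven step (IRT, importance, forest, any derived cut-off) inside stratified 10-fold cross-validation. Report held-out NPV, sensitivity and share cleared beside the apparent values, labelled as performance of the selection procedure and not of the one published form. If the cross-validation is repeated, base the exact interval on a pre-specified repeat, such as the first with a fixed seed, and call it approximate. Do not use the spread between repeats as the interval: its SD was 0.1-0.3 points against a true 0.65-1.15.
4. Label the short form's NPV, sensitivity and share cleared as applying only to people who passed the existing higher-risk screen. Higher-risk subjects are never tested, so sensitivity among everyone reporting an allergy cannot be estimated.

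**Cost.** Wording and computing; no new data. In the 3% forest illustration the reported NPV falls by 0.5-0.6 points against out-of-bag and 1.2-1.3 against resubstitution. The approximate interval is about 6-18% too narrow. At 1% reactivity there is about one reactor per fold, so precision is poor. Only about one fold in five chose the final form in the forest illustration, so the held-out figures do not validate that form; doing so would need new data.

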8.2 Sample Size Considerations

The sample size for this study was selected to have adequate study power to conclude a high NPV of the PCN (B-lactam) allergy history screening questionnaire in ruling out the presence of true PCN (B-lactam) allergy. To address the objective properly, we applied Steinberg's et al.³² approach to obtain the minimal sample size needed to achieve a lower 95% confidence bound for NPV that exceeds the NPV with a useless test at a fixed level of significance with a given study power. Based on this approach, the sample size calculation depends on the prevalence of PCN allergy in the population and among observed study participants and the sensitivity and specificity of the PCN allergy diagnostic kit (PRE-PEN®). To target at least 85% power at 5% of significant level, the listed sample sizes (see table) provide lower 95% confidence bounds for NPV under the following various assumptions:

- The true population prevalence with PCN allergy: 1%, 3%, 5%
- The observed % of PCN allergy in this study: 1%, 3%, 5%
- The PCN allergy diagnostic kit with sensitivity at least 85% and specificity 95%
- 5% of participants who report a PCN allergy history will have a high-risk allergy history and therefore will not proceed to skin testing.

Population prevalence of PCN allergy	Observed % of PCN allergy in study	Estimated NPV	The lower 95% confidence bound for NPV						
			99.0%	98.4%	97.9%	97.5%	97.3%	97.0%	95.0%
1%	1%	99.84%	1259	796	635	556	526	488	351
	3%	99.51%	420	265	212	185	175	163	117
	5%	99.18%	252	159	127	111	105	98	70
3%	1%	99.84%	8119	2964	1958	1559	1421	1259	759
	3%	99.51%	2707	988	653	520	474	420	253
	5%	99.18%	1624	593	392	312	284	252	152
5%	1%	99.84%	113000	9519	4770	3378	2950	2483	1259
	3%	99.51%	37547	3174	1590	1126	984	828	420

	5%	99.18%	22533	1905	954	676	590	497	252
--	----	--------	-------	------	-----	-----	-----	-----	-----

For example, with 3% PCN allergy prevalence in population and among observed study participants, the NPV for a useless test is 97%. A useful PCN (B-lactam) allergy history screening questionnaire should have the lower 95% confidence bound for NPV greater than 97%. Based on the list a minimum sample size of 988 subjects who reported to have PCN allergy history would provide an estimated NPV = 99.51% with 85% power to conclude that the NPV of the study allergy history screening questionnaire is least 98.4% at 5% significant level.

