5. GENERAL STATISTICAL ISSUES

All confidence intervals will be two-sided with 95% coverage. Likewise, all statistical tests will be two-sided and at 0.05 significance level.

Missing data will be treated as missing at random without imputation unless available evidence indicated that missing data is informative. Data at all non-missing time points will be used and included in relevant analyses.

All comparisons between treatment groups will be made without adjustment for multiple comparisons. All statistical analyses will be done using SAS® (SAS Institute Inc., Cary) Version 9.4.

6. Sample Size Consideration

The sample size for this study was selected to have adequate study power to conclude a high NPV of the PCN (B-lactam) allergy history screening questionnaire in ruling out the presence of true PCN (B-lactam) allergy. The approach proposed by Steinberg et al. (2009) is used to obtain the minimal sample size needed to achieve a lower 95% confidence bound for NPV that exceeds the result with a useless test at a fixed level of significance with a given study power. To target at least 85% power at 5% of significant level, the listed sample sizes (see table) provide lower 95% confidence bounds for NPV under the following various assumptions:

- The true population prevalence with PCN allergy: 1%, 3%, 5%
- The observed % of PCN allergy in this study: 1%, 3%, 5%
- The PCN allergy diagnostic kit with sensitivity at least 85% and specificity 95%
- 5% of participants who report a PCN allergy history will have a high-risk allergy history and therefore will not proceed to skin testing.

Population prevalence of PCN allergy	Observed % of PCN allergy in study	Estimate d NPV	The lower 95% confidence bound for NPV						
			99.0%	98.4 %	97.9 %	97.5 %	97.3 %	97.0 %	95.0 %
1%	1%	99.84%	1259	796	635	556	526	488	351
	3%	99.51%	420	265	212	185	175	163	117
	5%	99.18%	252	159	127	111	105	98	70
3%	1%	99.84%	8119	2964	1958	1559	1421	1259	759
	3%	99.51%	2707	988	653	520	474	420	253
	5%	99.18%	1624	593	392	312	284	252	152
5%	1%	99.84%	11600	9519	4770	3378	2950	2483	1259
	3%	99.51%	37547	3174	1590	1126	984	828	420

	5%	99.18%	22533	1905	954	676	590	497	252
--	----	--------	-------	------	-----	-----	-----	-----	-----

A sample of 988 subjects who reported to have PCN allergy history would provide an estimated NPV = 99.51% with 85% power to conclude that the NPV of the study allergy history screening questionnaire is least 98.4% at 5% significant level.

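### At 1% to 5% reactors, choosing the short questionnaire by highest NPV ranks candidate forms on differences of about 0.1 percentage point unless a cut-off and a sensitivity floor are set

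*SAP*

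**What the plan says.** The first primary objective ends in a short questionnaire of 4 to 6 items. SAP 7.3 and Protocol 8.4.1 build it in two steps. Item response theory and variable importance first show which items discriminate. The protocol would then "apply machine learning approaches (e.g., random forest approach via R packages of caret") and, as the SAP also puts it, "select a short post-study questionnaire that has the highest NPV among those possible short questionnaires with 4-6 selected questions".

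Neither document gives a vote cut-off, class weights or resampling, a minimum sensitivity, a minimum share labelled positive, a tie rule, or the number of items that pass the first step. Neither says whether NPV is computed on the training subjects or out of sample.

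The reactor rates come from the sample size section (SAP 6, Protocol 8.2): "The true population prevalence with PCN allergy: 1%, 3%, 5" per cent, and "The observed % of PCN allergy in this study: 1%, 3%, 5" per cent. The protocol adds that "with 3% PCN allergy prevalence in population and among observed study participants, the NPV for a useless test is 97" per cent.

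**The concern.** When few people react, a rule that labels everyone non-allergic already has an NPV of 1 minus prevalence. A random forest with a simple majority vote comes close to that rule at these rates, because few answer patterns contain more reactors than non-reactors. The forms then have almost the same NPV whatever questions they contain, and the highest value may be decided by one or two people. The stake is which questions enter the short form that clinics would use. Computing NPV out of sample does not cure this, since the near-ties below are already in out-of-bag values.

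**Working it through.** **1. The plan's own figure.** Inputs from SAP 6: "The PCN allergy diagnostic kit with sensitivity at least 85% and specificity 95" per cent; "5% of participants who report a PCN allergy history will have a high-risk allergy history and therefore will not proceed to skin testing"; "To target at least 85% power at 5% of significant level". Take prevalence 3% (population and observed) and lower bound 98.4%.

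- NPV = 0.97×0.95 / (0.97×0.95 + 0.03×0.15) = 0.9215/0.9260 = 99.51%.
- Test log[(1−sens)/spec] at fixed prevalence. Alternative: 0.15/0.95 = 0.1579. Null: (0.016/0.984)×(0.97/0.03) = 0.5257. Log ratio 1.203.
- n = (1.645+1.036)² × [0.85/(0.15×0.03) + 0.05/(0.95×0.97)] / 1.203² = 7.189×188.94/1.447 = 938.8. Divided by 0.95 this is 988.

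The 988 reproduces, with a one-sided 5% level.

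**2. Number of reactors.** 939×0.03 = 28 among those tested. Of these, 28×0.15 = about 4 are the false negatives implied by the 99.51%.

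**3. What a majority vote needs.** A vote above 0.5 requires a positive likelihood ratio above (1−p)/p. The plan's assumed accuracy gives 0.85/0.05 = 17.

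| Reactor rate | LR+ needed | LR+ at 85%/95% | PPV at 85%/95% |
|---|---|---|---|
| 1% | 99 | 17 | 14.7% |
| 3% | 32.3 | 17 | 34.5% |
| 5% | 19 | 17 | 47.2% |

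Even an answer as accurate as the plan's test falls on the non-allergic side at every planned rate.

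**4. How far forms differ in NPV.** Simulation: 950 tested, 10 candidate items, all 210+252+210 = 672 forms of 4 to 6 items, 100-tree forests, 0.5 vote, out-of-bag NPV, 6 to 16 data sets per scenario, 3% reactors. Item frequencies and odds ratios (OR) are assumptions; the documents give none.

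| True predictors | Forms flagging nobody, yes/no items | Same, graded items | Forms within 0.1 point of 97% | Share of true predictors in top form (random 0.50) |
|---|---|---|---|---|
| None | 81% | 20% | 98–100% | 0.52–0.64 |
| Three, OR 3 | 56–59% | 7–8% | 93–97% | 0.53–0.71 |
| Three, OR 5 | 47–50% | 5% | 83–93% | 0.68–0.80 |
| One item at 85%/95% | 41% | 9% | 56–70% | 1.00 |

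At OR 10 the last column was 0.83–0.94. On average, forms labelled 0.03% to 0.9% of people allergic. Up to OR 5, NPVs ran only from about 97.0% to 97.2–97.6%. With yes/no items at OR 3, 99.9% of forms lay within 0.1 point of the base rate at 1% reactors, and 92% at 5%.

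**5. What the ranking measure costs.** A second simulation had three true predictors among 10 items, all 252 five-item forms, and 9 to 12 data sets per scenario. It compared highest out-of-bag NPV with cross-validated AUC from ridge logistic regression. A random form keeps all three predictors 21/252 = 8% of the time.

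| Items | Reactors | OR | NPV rule keeps all three | AUC keeps all three |
|---|---|---|---|---|
| Graded | 3% | 3 | 13% | 67% |
| Graded | 3% | 5 | 56% | 100% |
| Graded | 5% | 3 | 29% | 100% |
| Graded | 5% | 5 | 50% | 92% |
| Yes/no | 3% | 3 | 8% | 33% |
| Yes/no | 3% | 5 | 14% | 92% |
| Yes/no | 5% | 5 | 17% | 92% |

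AUC did better in all 16 scenarios run. Each figure is rough: with 12 data sets, the standard error near 50% is √(0.25/12) = 14 points.

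**6. With the importance screen.** A third simulation (950 subjects, 10 yes/no items, a bagged majority-vote stand-in for the forest, 12 data sets per scenario) put 94–99% of forms within 0.1 point of the base rate. Both true predictors were kept 37–63% of the time by NPV, 42–81% by NPV after keeping the top seven items by importance, and 83–100% by AUC. For scale, a random five-item form keeps two given items 56/252 = 22% of the time from ten items, and 10/21 = 48% from seven if both pass the screen.

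**The case against.** - **The screen comes first.** A tight screen could do most of the work. With two predictors at OR 6, the top five items by a simple importance measure held both in 96% of 600 data sets at 1.5% reactors and 99% at 3%; at OR 3 the figures were 72% and 86%. This stands in part. The SAP sets no retention rule, the final choice is still by NPV, and the shortfall remained after a top-seven screen.
- **Graded items.** Protocol Appendix B grades symptoms by severity. That cuts exact ties sharply, but the near-ties remain.
- **Majority vote and random forest are not prescribed.** Random forest is an example and 0.5 is a software default. This stands: the gap is an unstated rule. A cut-off at the reactor rate reduced the forms within 0.1 point from 83–97% to 21–77%, and the top form then held 0.78–0.94 of the true predictors.
- **In-sample scoring.** Computed on the training subjects, with graded items at OR 5 and 3% reactors, NPVs spread from 97.05% to 99.00%, 3.7% of forms lay within 0.1 point, and the top form held 0.89 of the true predictors. So the near-ties belong to out-of-sample NPV. The SAP does not say which it means, and in-sample NPV is optimistic as a measure of performance.
- **The comparison favours AUC.** It changes classifier and measure together, on data generated from item odds ratios, which suits logistic regression. The size of the gap should be read with that in mind.

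**Conclusion.** The point holds as a gap in the plan. With highest NPV as the only criterion and a default majority vote, forms are ranked on values that hardly leave 1 minus prevalence, and informative questions are kept less often than under a threshold-free measure. This rests on a 0.5 vote, out-of-sample NPV, weak-to-moderate predictors, assumed item frequencies and few simulated data sets.

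Three stronger readings are tempting and not supported:

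- A reader might infer that the questions are picked close to at random. That fits no signal, and roughly OR 3 or very low rates. With stronger predictors the rule clearly beats chance, and it found a single 85%/95% item every time.
- A reader might infer from the 99.51% that only about five reactors are expected. That NPV comes from 3% prevalence, so about 28 reactors with 4 to 5 of them missed.
- A reader might infer that the primary results are undermined. The listed primary outcome measures, NPV of the full questionnaire and prevalence of reactivity, do not use this selection.

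It should be fixed before analysis because the short form is the product of a primary objective. No ranking rescues very sparse data: at 0.5% reactors, below the planned range, NPV kept all three predictors 7–8% of the time and AUC 18–25%.

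**What to change.** In SAP 7.3 and Protocol 8.4.1:

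1. Keep the item response theory and importance screen, and state how many items pass it.
2. Rank the candidate 4 to 6 item forms by cross-validated AUC, from penalised (ridge or Firth) logistic regression or from the vote fractions of a class-balanced random forest.
3. For the chosen form, set the cut-off by a pre-stated sensitivity target.
4. Report its cross-validated NPV together with sensitivity and the share labelled negative.

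If ranking by NPV is kept, the least that is needed is a stated cut-off, a sensitivity floor, a tie rule, and whether NPV is computed out of sample.

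The cost is wording and programming, with no new data. The downside is that the chosen form may not have the highest apparent NPV in the sample.
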